Exploratory Endpoints: Comparison of the proportion of subjects in each population who have at least a 1-grade improvement in the C-CAT on Day 84 versus baseline. Comparison of the proportion of subjects in each population who have at least a 1-grade improvement in the S-CAT on Day 84 versus baseline. Comparison of the proportion of subjects in each population who have at least a 1-grade improvement in both the C-CAT and S-CAT (Day 84 versus baseline). Comparison of the proportion of subjects in both populations who have at least a 2-grade improvement in both the C-CAT and S-CAT (Day 84 versus baseline). Comparison of the reduction in SMF thickness measured with caliper (Day 84 versus baseline) in a Chinese vs. non-Chinese population Safety of RZL-012 in the treatment of SMF reduction. Physicians Global Assessment SMF improvement using the Global Aesthetic Improvement Scale (GAIS). Subject Global Self-Assessment SMF improvement using the Subject Global Assessment of Change Scale. SMF improvement using the subject's satisfaction questionnaires. SMF improvement using Subject's Impact Questionnaire. This is a Phase 2, open-label study that will consist of a screening period, baseline period in **Study Design** which subjects will receive a single treatment session and a follow-up period. The single treatment session will consist of multiple injections of RZL-012 for a maximal total dose of 270 mg into the submental area under the chin. Blood samples will be collected from all subjects for PK analyses in the first 30 hours after dosing. Subjects will thereafter be monitored for safety and efficacy for at least 84 days. Sample Size 20 subjects (10 Chinese and 10 non-Chinese): No formal sample size calculation was performed. The planned sample size of 10 subjects per study arm is sufficient to compare the PK profile between the 2 study populations. Study Adult volunteers age 18 to 65 years who have consented to participate in this study and seek submental fat reduction. **Population Main Inclusion** For a subject to be eligible for this study, he or she must meet all of the following criteria: Criteria Is a male or female subject between the ages of 18 and 65 years, inclusive. Has body mass index (BMI) between $>22 \text{ kg/m}^2$ and $<40 \text{ kg/m}^2$. If enrolled for Chinese arm, subjects have to be ethnically pure, i.e., were born in China (Certificate birth) with all four grandparents being Chinese or at least have parents that were born in China (Certificate birth of the parents). Has a SMF bulge that is contiguous and fits to 32±4 injections sites according to a grid with 1 centimeter (cm) distance between injection points. Has grade 3 to 4 of SMF as rated by both the C-CAT and S-CAT. Has a visible or large pocket of submental fat- according to physician global assessment. Has stable weight, with no fluctuation of >5 kg in the past 12 months. If female, is not pregnant or breastfeeding based on the following: agree to the use of highly effective contraceptive methods for at least 2 weeks before baseline until 4 weeks after the last day of study drug and a negative

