- 23. Current participation or participation within three (3) months prior to the start of this study in a drug or other investigational research study.

Dosage and Administration of Study Drug

All subjects will receive a single multi-injection session of RZL-012 in accordance with the table below:

Number of subjects	N=20
RZL-012 dose	240mg±30mg/4.8 ±0.6 mL
RZL-012 Dose (mg)/volume (mL) per single injection	7.5mg/0.15mL
Number of Injections per subject	32±4

Subjects will undergo a single treatment session with 32 ± 4 injections. The total number of injections will be 32 ± 4 with a dose of 240 ± 30 mg RZL-012. Each injection point will be dosed with 7.5 mg RZL-012 in a volume of 0.15 mL/injection site. The total injection volume for all groups will be 4.8 mL ±0.6 .

Subjects will be injected with RZL-012 perpendicularly (90°) to the skin. An ice pack will be placed on the injected area for pain relief immediately after injection. Subjects will remain seated in the injection position for an additional 10 minutes after dosing.

The injection pattern will be based on a submental area shaped grid in which the distance between rows and columns will be 1 cm, as seen in the figure below. The Investigator will choose 32±4 sequential points on the grid that will mark the injected area according to SMF fullness and convexity. The treatment area boundary: superiorly by a line 1 cm inferior to the mandibular margin, laterally by the sternocleidomastoid muscles, and inferiorly by the hyoid bone.

	\$ - \(\tag{5} \)
Safety	AEs will be collected and reviewed to evaluate the safety and tolerability of RZL-012. AE collection will begin after dosing and will end at discharge assessments on Day 84. For subjects for whom AEs are unresolved by Day 84, an unscheduled visit will be set 6-8 weeks after Day 84 to verify the resolution of the AE. Other safety measures will include vital sign measurements, Lab parameters follow up on Day 1, 7, 28 and 84 following injection, ECG, and treatment area evaluation. Treatment area evaluations including, but not limited to evaluation of edema, bruising, dysphasia, dysphonia, erythema, dyspigmentation, induration, numbness, pain, paresthesia, , pruritus, skin ulceration and necrosis, injury to the marginal mandibular nerve, vascular and nerve injury and tissue damage to nearby vulnerable anatomic structures. Concomitant medications will be recorded.

T	

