Statistical Analysis	A sample size of 20 subjects will be included in the study. All will be injected with the same dose of RZL-012. A total of 10 subjects will be Chinese and 10 subjects will be non-Chinese.
	All measured variables and derived parameters will be listed individually and, if appropriate, tabulated by descriptive statistics.
	For categorical variables, summary tables will be provided giving sample size, absolute and relative frequency, and 95% confidence interval (CI) for proportions by study arm.
	For continuous variables, summary tables will be provided giving sample size, arithmetic mean, standard deviation, coefficient of variations (CV%), median, minimum and maximum, and 95% CI for means of variables by study arm.
	Primary endpoint:
	A total of 10 subjects per group will be used to compare between PK profile of both populations.
	Individual plasma PK parameters will be listed by study arm and summarized in tables presenting sample size (N), mean, Standard deviation, Standard Error, Median, minimum and maximum values, Coefficient of variation (CV%) and 95% CI (Confidence Interval) for means of variables by treatment.
	PK assessments will be compared between the 2 study populations.
	Graphical displays will be generated presenting mean concentration by study arm as well as individual graphs per subject.
	Exploratory endpoints:
	The difference between study groups in proportion of subjects who have 1-grade improvement in the C-CAT, S-CAT, and who have 1-grade and 2-grade improvement in both C-CAT and S-CAT on Day 84 versus baseline will be tested using a two-sided test of equality of binomial proportions at the alpha=0.05 level of significance.
	All other endpoints will be tested using a two-sided test at the alpha=0.05 level of significance.
	The SMF improvement using the Global Aesthetic Improvement Scale (GAIS), the physician Global Assessment of Change Scale, Subjects Global Self-Assessment of Change Scale, Subject Global Assessment of Change Scale, the subject's satisfaction questionnaires, and the subjects's impact questionnaire will be summarized at each timepoint and by study group.
	The data will be analyzed using the SAS version 9.4 (SAS Institute, Cary North Carolina).
Study Duration	It is planned that each subject will participate in the study for four (4) months, which comprises a screening period, baseline/treatment period, and follow up period.
Study Centers	Single center

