4.0 STUDY DESIGN

4.1 Overall Design

This is a Phase 2, open-label study that will consist of a screening period, baseline period in which subjects will receive a single treatment session of RZL-012 and a follow-up period. The single treatment session will consist of multiple injections of RZL-012 into the submental area under the chin. Blood samples will be collected from all subjects for PK analyses in the first 48 hours after dosing. Subjects will thereafter be monitored for safety and efficacy for at least 84 days.

All subjects will be treated with a total dose of 270 mg RZL-012.

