5.0 STUDY POPULATION

5.1 Inclusion Criteria

For a subject to be eligible for this study, he or she must meet **all** of the following inclusion criteria:

- 1. Is a male or female subject between the ages of 18 and 65 years, inclusive.
- 2. Has body mass index (BMI) between $>22 \text{ kg/m}^2$ and $<40 \text{ kg/m}^2$.
- 3. If enrolled for Chinese arm, subjects have to be ethnically pure, i.e., Chinese passport holders with all four grandparents being Chinese.
- 4. Has SMF bulge that is contiguous and fits to 32±4 injections sites according to a grid with 1 centimeter (cm) distance between injection points.
- 5. Has grade 3 to 4 of SMF as rated by both the C-CAT and S-CAT.
- 6. Has a visible or large pocket of submental fat- according to physician global assessment.
- 7. Has stable weight, with no fluctuation of >5 kg in the past 12 months.
- 8. If female, is not pregnant or breastfeeding based on the following:
 - a. agree to the use of highly effective contraceptive methods for at least 2 weeks before baseline until 4 weeks after the last day of study drug and a negative serum pregnancy test (β-hCG) at screening and negative urine pregnancy test at baseline; or
 - b. is of nonchildbearing potential defined as clinically infertile as the result of surgical sterilization (hysterectomy, bilateral tubal ligation, and/or bilateral oophorectomy); or
 - c. is confirmed postmenopausal status (defined as either having amenorrhea for ≥ 12 consecutive months without another cause and documented serum follicle-stimulating hormone (FSH) level > 40 mIU/mL or another documented medical condition (e.g., was born without a uterus))

NOTE: The following are considered highly effective contraceptive methods: hormonal oral contraceptives, injectables, and patches; intrauterine devices; double-barrier methods (synthetic condom, diaphragm, or cervical cap used with spermicidal foam, cream, or gel); and male partner sterilization.

- 9. If male (with or without vasectomy), agree to the use of highly effective contraceptive methods as listed above in criteria 7 as well as to use a barrier method, e.g. condom, from study checkin until 7 days after the last day of study drug.
- 10. Is willing to avoid strenuous exercise for seven (7) days post treatment.
- 11. Is able to adhere to the visit schedule and protocol requirements and be available to complete the study.

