6.1.2 Dosing and Administration

[figure not shown]
Subjects will undergo a single treatment session with 36 injections of 7.5 mg RZL-012 each for a total RZL-012 dose of 270 mg. The total injection volume for all groups will be 4.8 mL±0.6.

Subjects will be injected with RZL-012 perpendicularly (90°) to the skin. An ice pack will be placed on the injected area for pain relief immediately after injection. Subjects will remain seated in the injection position for an additional 10 minutes after dosing.

The injection pattern will be based on a submental area shaped grid in which the distance between rows and columns will be 1 cm, as seen in Figure 1 below. The Investigator will choose 32±4

sequential points on the grid that will mark the injected area according to SMF fullness and convexity. The treatment area boundary: superiorly by a line 1 cm inferior to the mandibular margin, laterally by the sternocleidomastoid muscles, and inferiorly by the hyoid bone.

Figure 1 Submental Injection Pattern

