6.2 Preparation/Handling/Storage/Accountability

The RZL-012 solution is supplied ready to use. The RZL-012 kits, each comprised of 2 vials, should be stored in the site pharmacy or clinic at monitored room temperature conditions (22 ± 7 °C) and protected from light. They should be kept in a secure location physically separated from standard clinic or office drug supplies.

RZL-012 is administered to the subject on the study site by the study investigator. The vials should be manually shaken prior to injection.

The following procedures prior to injection will be applied:

The following procedures prior to injection into the SMF will be applied:

- 1. The lower face and anterior neck will be cleaned with an appropriate topical antiseptic.
- 2. Ice/cold pack or topical local anesthesia (i.e., lidocaine cream) may be used prior to drug administration to enhance subject's comfort.
- 3. The treatment area will be bounded superiorly by a line 1 cm inferior to the mandibular margin, laterally by the sternocleidomastoid muscles, and inferiorly by the hyoid bone.
- 4. Injection grid pattern will be applied by pressing the grid firmly onto the clean, dry skin, with the printed grid pattern facing the skin. The grid paper backing will be thoroughly wetted with a cotton pad soaked with sterile water. After 15 seconds, the grid cover will be peeled off.
- 5. An area of 32±4 adjacent injection points will be determined following the Investigator's evaluation.

- 6. Syringes will be filled with 1 mL RZL-012 or placebo and the number of syringes will be compatible with the total volume of injection. Up to six (6) syringes for a total volume of 5.4 mL will be used.
- 7. All injections will be administered perpendicularly in 90 degrees, using a 1 mL Luer-lock syringe and a 27G/29G x 1/2" needle, respectively.
- 8. The hole of the needle should be pointing into the middle of fat layer and the injection direction should be towards the earth. An attempt to pull the plunger should be made prior to injecting to ensure no blood is coming out. If so, the plunger should be pushed down to inject 0.15 ml the medicine. The formulation is viscous; therefore, resistance is expected during injection.
- 9. Immediately following completion of the injections, an ice/cold pack will be applied for immediate pain relief. It will be held by the subject for at least two (2) minutes.
- 10. The Investigator will record the number of injections administered for each subject.

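### The protocol gives two dosing rules, 270 mg for everyone and 210 to 270 mg by submental fullness, and the SAP names no dose summary by arm

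*Protocol*

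**What the plan says.** Three statements in the protocol fix the dose.

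- Section 4.1: "All subjects will be treated with a total dose of 270 mg RZL-012".
- Section 6.1.2, first sentence: "Subjects will undergo a single treatment session with 36 injections of 7.5 mg RZL-012 each for a total RZL-012 dose of 270 mg".
- Synopsis, statistical analysis row: "All will be injected with the same dose of RZL-012". This one gives neither milligrams nor an injection count.

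The other dosing text sets a range.

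- Synopsis, study design row: multiple injections "for a maximal total dose of 270 mg", so 270 mg is a ceiling. The SAP study design text says the same.
- Synopsis, dosage row, repeated in the SAP: "The total number of injections will be 32 ± 4 with a dose of 240 ± 30 mg RZL-012".
- Section 6.1.2, second sentence: "The total injection volume for all groups will be 4.8 mL±0.6". The section then has the investigator pick 32±4 grid points by fullness and convexity.
- Section 6.2: the investigator sets the number by fullness, with a floor of 28 and a cap of 36.
- Inclusion 4: the bulge "fits to 32±4 injections sites according to a grid". Exclusions 6 and 7 remove bulges too large or too small for that number.

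On data, 6.2 item 10 says: "The Investigator will record the number of injections administered for each subject". Later in 6.2, count and volume go into the medical records.

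The SAP's primary analysis lists Cmax, Tmax, AUC0-t, AUC0-inf, the elimination constant and half-life, summarised by arm. Its endpoint list also has AUCpartial, which the analysis section omits. Neither place names a dose-normalised parameter, and the SAP's list of baseline tables contains neither dose nor injection count.

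**The concern.** The dosing rule is wrong as written in at least one place. An investigator who follows 4.1 and the opening of 6.1.2 departs from 6.2, and the reverse also holds. Inclusion 4 admits a subject whose bulge fits only 28 sites, and for that subject the two texts give different treatments.

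The second issue concerns the primary objective. Under the range rule, dose depends on an anatomical feature. The arms are defined by ethnicity and not by randomisation. If mean injection counts differed between arms, raw Cmax and AUC could show a difference that is only dose, or hide one that is real. The SAP commits to no output by which a reader of the PK table could tell.

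**Working it through.** **1. Reproduce the plan's figures.** Inputs: 7.5 mg and 0.15 mL per injection, 32±4 injections (synopsis and SAP).

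- 28 injections: 28 × 7.5 = 210 mg; 28 × 0.15 = 4.2 mL
- 32 injections: 240 mg; 4.8 mL
- 36 injections: 270 mg; 5.4 mL

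These match 240±30 mg and 4.8±0.6 mL exactly. So 270 mg is the top of the range, as the synopsis design row says.

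**2. Difference for one subject between the two texts.**

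- Fits 28 sites: 36 − 28 = 8 more injections, 8 × 7.5 = 60 mg, 270/210 = 1.286 (29% more).
- Fits 32 sites: 4 more injections, 30 mg, 270/240 = 1.125 (12.5% more).
- Fits 36 sites: no difference.

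**3. What a dose imbalance could do to the PK comparison.** Assume exposure proportional to dose and no true PK difference. The apparent ratio is then the ratio of mean doses.

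- Mean counts 33 v 31: 247.5/232.5 mg = 1.065
- Mean counts 34 v 30: 255/225 mg = 1.133

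**4. Scale against sampling error.** Neither document gives a PK coefficient of variation or plans a ratio confidence interval, so CVs of 20%, 30% and 50% are assumed, for scale only. With 10 per arm and t(18) = 2.101:

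SE = sqrt(ln(1 + CV²)) × sqrt(2/10); 95% CI factor = exp(2.101 × SE); share of half-width = ln(ratio)/(2.101 × SE).

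| Assumed CV | SE (log) | 95% CI factor | 33 v 31 as share | 34 v 30 as share |
|---|---|---|---|---|
| 20% | 0.0886 | 1.20 | 34% | 67% |
| 30% | 0.131 | 1.32 | 23% | 45% |
| 50% | 0.211 | 1.56 | 14% | 28% |

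Both examples lie inside the half-width throughout.

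**5. How likely are such imbalances by chance?** The documents give no distribution of counts. Assume a uniform spread over 28 to 36: SD = sqrt((9² − 1)/12) = 2.58. The SE of the difference in mean count is 2.58 × sqrt(2/10) = 1.15 injections. A gap of 2 (33 v 31) is 2/1.15 = 1.7 SE, and a gap of 4 (34 v 30) is 4/1.15 = 3.5 SE. The larger gap would in effect need a systematic anatomical difference between the arms.

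**6. Does normalising gain precision?** Under the same uniform assumption the dose CV is 2.58/32 = 8.1%. Its share of total variance is (0.081/CV)² = 16%, 7% and 3% at CVs of 20%, 30% and 50%. The gain is small. The use of normalisation is to show or rule out a systematic imbalance.

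**The case against.** Section 6.2 is the step-by-step procedure and is explicit on 28 to 36 injections by fullness. Eligibility uses the same numbers, the study has a single center, and the study investigator gives the injections. Over-treating a 28-site subject would mean following one sentence of 6.1.2 against the rest of that section and all of 6.2. This stands as a limit on likelihood. It does not remove the conflict, because 6.1.2 is the section headed as the dosing instruction.

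A reader might also infer more than the documents support.

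- *That different sites would dose differently.* There is one center.
- *That a subject could be dosed above the plan's limit.* Every reading stays at or below 270 mg, a dose already given to a Phase 2b arm.
- *That the volume sentence in 6.1.2 flatly contradicts the one before it.* The 5.4 mL from 36 injections lies within 4.8±0.6 mL. The sentence implies a range, but it does not exclude 36 injections.
- *That dose data would be lost.* Counts and volumes are recorded. The SAP lists all measured variables, tabulates them where suitable, and allows further PK parameters when judged necessary. These clauses leave the choice open without committing to it.

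On the PK side, the comparison is descriptive and the SAP presents p-values only to indicate trends. The dose tables are therefore a supplementary improvement and not the repair of a failed test.

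**Conclusion.** The dosing contradiction holds and is the main point. Section 4.1, the opening of 6.1.2 and the synopsis statistics row cannot all stand beside a per-subject range of 210 to 270 mg. The difference for one subject runs from nothing at 36 sites to 60 mg (29%) at 28 sites. This rests on the documents' own figures alone.

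The analysis gap is real but secondary. It is tempting to conclude that the Chinese v non-Chinese PK comparison is biased by dose. The documents do not support that: nothing in them shows that fullness differs by arm, and the shared eligibility limits (grade 3 to 4, 28 to 36 sites) cap any difference. The apparent ratios of 1.065 and 1.133 are illustrations that assume dose proportionality, and the comparison with sampling error rests on assumed CVs. The size of any bias is unknown and probably below sampling noise.

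**What to change.** **Protocol.** Change 4.1, the first sentence of 6.1.2 and the synopsis statistics row to 32±4 injections of 7.5 mg, 240±30 mg, maximum 270 mg, with the same dosing rule in both arms. Eligibility is untouched, since inclusion 4 and exclusions 6 and 7 already use 32±4. The alternative, 36 injections for everyone, would also remove the conflict, but it would narrow eligibility and mean rewriting 6.2 and the SAP. The sponsor should confirm its intent.

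**SAP (secondary).** Derive actual dose as 7.5 mg × recorded injections and tabulate injections and dose by arm. Report dose-normalised Cmax, AUC0-t, AUC0-inf and, if it is calculated, AUCpartial by arm as a supportive analysis beside the raw values, which remain the main result. State the dose-proportionality assumption. Leave Tmax, λz and half-life unadjusted.

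**Cost.** Three wording changes, one derived variable, one dose table and one supportive PK table. No new measurement is needed, but 6.2 places the count in medical records, so confirm that the eCRF captures it. The downside is that normalisation relies on dose proportionality, which the documents do not establish, and adds little precision.

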4.2 Rationale for Study Design

Since all subjects will receive the same study treatment, the study will employ an open-label design.

4.3 Rationale for Study Dose

The Phase 2b study (RZL-012-SMF-P2b-US-001) demonstrated that a single treatment session of RZL-012 at a maximal dose of 270 mg into the subcutaneous tissue of the submental area reduces fat and improves appearance of this area.

5.0 STUDY POPULATION

5.1 Inclusion Criteria

For a subject to be eligible for this study, he or she must meet **all** of the following inclusion criteria:

- 1. Is a male or female subject between the ages of 18 and 65 years, inclusive.
- 2. Has body mass index (BMI) between $>22 \text{ kg/m}^2$ and $<40 \text{ kg/m}^2$.
- 3. If enrolled for Chinese arm, subjects have to be ethnically pure, i.e., Chinese passport holders with all four grandparents being Chinese.
- 4. Has SMF bulge that is contiguous and fits to 32±4 injections sites according to a grid with 1 centimeter (cm) distance between injection points.
- 5. Has grade 3 to 4 of SMF as rated by both the C-CAT and S-CAT.
- 6. Has a visible or large pocket of submental fat- according to physician global assessment.
- 7. Has stable weight, with no fluctuation of >5 kg in the past 12 months.
- 8. If female, is not pregnant or breastfeeding based on the following:
 - a. agree to the use of highly effective contraceptive methods for at least 2 weeks before baseline until 4 weeks after the last day of study drug and a negative serum pregnancy test (β-hCG) at screening and negative urine pregnancy test at baseline; or
 - b. is of nonchildbearing potential defined as clinically infertile as the result of surgical sterilization (hysterectomy, bilateral tubal ligation, and/or bilateral oophorectomy); or
 - c. is confirmed postmenopausal status (defined as either having amenorrhea for ≥ 12 consecutive months without another cause and documented serum follicle-stimulating hormone (FSH) level > 40 mIU/mL or another documented medical condition (e.g., was born without a uterus))

NOTE: The following are considered highly effective contraceptive methods: hormonal oral contraceptives, injectables, and patches; intrauterine devices; double-barrier methods (synthetic condom, diaphragm, or cervical cap used with spermicidal foam, cream, or gel); and male partner sterilization.

- 9. If male (with or without vasectomy), agree to the use of highly effective contraceptive methods as listed above in criteria 7 as well as to use a barrier method, e.g. condom, from study checkin until 7 days after the last day of study drug.
- 10. Is willing to avoid strenuous exercise for seven (7) days post treatment.
- 11. Is able to adhere to the visit schedule and protocol requirements and be available to complete the study.
- 12. Is willing and able to sign an Institutional Review Board (IRB) approved informed consent form (ICF) indicating that they are aware of the investigational nature of the study.

